14.1.2 Handling Missing Data

Primary and secondary objectives will be analyzed using the FAS. The FAS includes all subjects, using the intention-to-treat principle, who have an attempted device implant. All attempts will be made to minimize missing data. For diary-based metrics, missing is defined as any diary which has a total length of less than 48 hours, as defined in section 14.1.5. The OAB-q may be missing if the HRQL Total cannot be calculated; scoring details are found in section 14.5.4. If 5% of the data or fewer are missing for the analysis, no imputation will be used and the data will be analyzed using the Complete Case analysis set²⁵. Otherwise, if missing data are observed, imputation will be used for the primary and secondary objectives.

The primary objective imputation will be done using multiple imputation (MI). Predictive mean matching multiple imputation will be used for each variable. First, multiple imputation will be applied to impute missing values in average daily UUI episodes. Unless model errors dictate otherwise, each model will consider Baseline and Month 1, Month 2, Month 3, and Month 6 variables for the UUI episodes variable and demographic variables of age, gender, history of pregnancy, and BMI. The fully conditional specification (FCS) method within SAS (version 9.4 or higher) with 30 repetitions and 100 burn-in

iterations will be used for imputation. No limits will be defined for imputed values. Following imputation, the 6-month outcome data will be converted to the appropriate endpoint (i.e., change from baseline/UUI responder). The estimate and variance of the mean proportion of subjects considered a UUI responder will be determined for each imputation dataset. For the primary objective, the mean and variance for the proportion will be determined using MI analysis methods and the objective will be tested using a Z-test comparing the observed responder rate to the primary objective performance goal of 40%.

For the secondary objectives, the following imputation steps will be taken:

- For secondary objectives related to UUI episodes, the imputation datasets created for the primary objective will be used. For OAB-q HRQL, UF episodes, and urgency, a new set of imputation datasets will be created following the same methods as the primary objective but replacing UUI episodes with OAB-q HRQL, UF episodes, or urgency score.

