- After imputation, the normality for the outcome metric will be checked through Shapiro-Wilk test for each imputation dataset. If $p\text{-value} > 0.05$ for at least 15 imputed datasets (half of the total), it will be considered that the data are normally distributed. In this case, the mean and standard error of the outcome metric will be calculated within each imputed dataset, and then combined using MI analysis methods. The mean and standard error of the outcome metric will be reported, and the objective will be tested with a t-test.
- If the distribution of outcome metric is non-normal ($p\text{-values} \leq 0.05$ in more than 15 of the imputed datasets), MI will not be used. Instead, last observations carried forward (LOCF) will be applied, with the imputed dataset tested using the Wilcoxon signed-rank test.

Sensitivity analyses will be completed for the primary and secondary objectives including subjects who received a TNM implant (“All Implanted Analysis”), using only subjects with outcome data at baseline and follow-up (“Complete Case Analysis”), and using only those complete case subjects who received stimulation (“As Treated Analysis”).

Comprehensive descriptions of subject accountability and missing data will be provided.

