## **7.4 Handling of Missing, Unused, and Spurious Data and Dropouts**

Primary and secondary objectives will be analyzed using the FAS. The FAS includes all subjects, using the intention-to-treat principle, who have an attempted device implant. All attempts will be made to minimize missing data. For diary-based metrics, missing is defined as any diary which has a total length of less than 48 hours, as defined in section 7.2.2. The OAB-q may be missing if the HRQL Total cannot be calculated; scoring details are found in section 7.9.2.4. If 5% of the data or fewer are missing for the analysis, no imputation will be used, and the data will be analyzed using the Complete Case analysis set (Buhi 2008). Otherwise, if missing data are observed, imputation will be used for the primary and secondary objectives.

The primary objective imputation will be done using multiple imputation (MI). Predictive mean matching multiple imputation will be used for each variable. First, multiple imputation will be applied to impute missing values in average daily UUI episodes. Unless model errors dictate otherwise, each model will consider Baseline and Month 1, Month 2, Month 3, and Month 6 variables for the UUI episodes variable and demographic variables of age, gender, history of pregnancy, and BMI. The fully conditional specification (FCS) method within SAS (version 9.4 or higher) with 30 repetitions and 100 burn-in iterations will be used for imputation. No limits will be defined for imputed values. Following

imputation, the 6-month outcome data will be converted to the appropriate endpoint (i.e., change from baseline/UUI responder). The estimate and variance of the mean proportion of subjects considered a UUI responder will be determined for each imputation dataset. For the primary objective, the mean and variance for the proportion will be determined using MI analysis methods and the objective will be tested using a Z-test comparing the observed responder rate to the primary objective performance goal of 40%.

For the UUI, UF, and OAB-Q secondary objectives, the following imputation steps will be taken:

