For the secondary objective related to urgency using the UPS, the imputation datasets will be created using multiple imputation (MI). Logistic regression multiple imputation will be used for each variable which accounts for the ordinal nature of the UPS. First, multiple imputation will be applied to impute missing values in UPS. Unless model errors dictate otherwise, each model will consider Baseline, Month 3, and Month 6 variables for the UPS variable and demographic variables of age, gender, history of pregnancy, and BMI. The fully conditional specification (FCS) method within SAS (version 9.4 or higher) with 30 repetitions and 100 burn-in iterations will be used for imputation. Imputed values will be required to be 1, 2, or 3 to match the original scale. After imputation, the mean and standard error of the change from Baseline to Month 6 in UPS will be calculated within each imputed dataset, and then combined using MI analysis methods. The mean and standard error will be reported, and the objective will be tested with a t-test.

Sensitivity analyses will be completed for the primary and secondary objectives including subjects who received a TNM implant (“All Implanted Analysis”), using only subjects with outcome data at baseline

and follow-up (“Complete Case Analysis”), and using only those complete case subjects who received stimulation (“As Treated Analysis”).

[REDACTED] Comprehensive descriptions of subject accountability and missing data will be provided.

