**Analysis Methods:** The analysis for UPS will be summarized for baseline, at 6 months after implant, and for the change from baseline. If 5% of the data or fewer are missing for the analysis, no imputation will be used, and the objective will be tested using a paired t-test following the multiple testing strategy described in section 7.5. If more than 5% of the data are missing, missing data will be imputed as specified in section 7.4. If non-normality of the data is detected via a significant ( $p < 0.05$ ) Shapiro-Wilk test, a Wilcoxon signed-rank test will replace the t-test.

**Determination of Subjects/Data for Analysis:** The UPS analysis will include all subjects from the Full Analysis Set (i.e., all implant attempted subjects) as defined in section 7.1.3 as all subjects are expected to have urgency.

**Supportive and Sensitivity Analyses:** There are no requirements or expectations for the results of the supporting and sensitivity analyses.

To assess the robustness of the objective results under the influence of missing data, sensitivity analyses will be conducted using alternative missing data methods. The first sensitivity analysis will be completed including subjects from the Secondary Objective (UPS) Complete Case analysis set. This analysis set will be used for a second sensitivity analysis which will be completed including only subjects who received stimulation ('As treated analysis') at the 6-month follow-up visit. A third sensitivity analysis will be performed excluding those subjects who report limited problems with urgency, as reported by a baseline score of 3 on the UPS. A final complete case sensitivity analysis will be performed comparing the change in urgency to a performance goal of 0.4.

A supportive analysis will be completed summarizing the percentage of subjects in each category at each visit. The change in UPS will be further categorized as improvement (1-2 point improvement), no change, and worsening (1-2 point worsening), with the number and percentage of subjects summarized for each category.

To test the change in UPS using an alternative statistical analysis method, a supportive analysis will be completed recategorizing the values at each visit as into “not able to hold urine” (response level 1) and “able to hold urine” (levels 2/3). Change from baseline to Month 6 will be tested using Fisher’s exact test for the 2x2 contingency table.

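### With more than 5% of UPS data missing, SAP 7.4, SAP 7.9.2.3 and protocol 14.1.2 do not agree on the confirmatory urgency test

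*SAP*

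**What the plan says.** **5% or fewer missing.** SAP 7.9.2.3 uses complete cases, and "the objective will be tested using a paired t-test following the multiple testing strategy described in section 7.5". If Shapiro-Wilk gives p<0.05, "a Wilcoxon signed-rank test will replace the t-test". Protocol 14.5.3 has the same rule.

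**More than 5% missing, SAP.** SAP 7.9.2.3 refers onward: "If more than 5% of the data are missing, missing data will be imputed as specified in section 7.4". The Shapiro-Wilk sentence comes directly after this and names no branch. SAP 7.4 introduces its own Shapiro-Wilk and LOCF steps with "For the UUI, UF, and OAB-Q secondary objectives, the following imputation steps will be taken", a list that leaves UPS out. UPS has a separate paragraph: logistic-regression imputation, 30 repetitions, imputed values limited to 1, 2 or 3, results combined across datasets, and then "The mean and standard error will be reported, and the objective will be tested with a t-test".

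**More than 5% missing, protocol.** Protocol 14.1.2 keeps urgency in the common route: "For OAB-q HRQL, UF episodes, and urgency, a new set of imputation datasets will be created following the same methods as the primary objective". Shapiro-Wilk is run on each imputed dataset. If more than 15 of the 30 have p≤0.05, multiple imputation is abandoned: "Instead, last observations carried forward (LOCF) will be applied, with the imputed dataset tested using the Wilcoxon signed-rank test".

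**Hypothesis and power.** SAP 7.9.2.3 states H0: mu = 0, with mu the change in UPS score. It bases power on a two-sided one-sample t-test.

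**The concern.** SAP 7.5 makes this test the evidence for an effect on urgency, one of the three symptoms that support the OAB indication. The UPS p-value also enters the Hochberg procedure, which needs exactly one p-value per objective. SAP 7.5 leaves the method to each objective's own analysis section. For UPS that section points to 7.4 and then adds a rule that 7.4 does not contain, and nothing says which has precedence. The study is open-label and single-arm, and the sponsor's statisticians do the analysis, so the results of more than one route could be seen before it is settled which section governs.

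The normality check also does no real work for this endpoint. A score with so few values cannot look normal at this sample size, so the test named as the default would not be used wherever the check applies. The replacement, the signed-rank test, addresses the mean only if the changes are symmetric, while the hypothesis and the power statement both concern the mean.

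**Working it through.** **1. The plan's own figures.** Inputs from SAP 7.9.2.3: n=121, mean 0.50, SD 0.80, two-sided alpha 0.013 to 0.05. The noncentrality is sqrt(121) × 0.50/0.80 = 11 × 0.625 = 6.875. Noncentral-t power with 120 df is 99.9999% at alpha 0.05 and 99.9992% at alpha 0.013, in line with the stated 99% or more. The minimum detectable change at alpha 0.05 is 0.238 if 90% power is assumed (the plan does not state the power here), which matches the stated 0.24.

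**2. Where the branch changes.** 0.05 × 121 = 6.05. Six missing values are 6/121 = 4.96% and seven are 7/121 = 5.79%, so seven missing values open the imputation branch. At the cap of 130 implants, 0.05 × 130 = 6.5, so the number is again seven.

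**3. Whether the switch fires.** The item has three levels, so change can be −2, −1, 0, 1 or 2. The documents give no category probabilities, so these were assumed: six sets with mean 0.50 and SD 0.80, and five null or small-effect sets. Shapiro-Wilk rejected at 0.05 in 100% of samples for all 11 sets (2,000 samples each at n=121 and n=115, 1,000 at n=60). A grid search over count patterns for the most normal-looking data gave a largest p-value of 1.6 × 10⁻⁶ at n=121 and 2.6 × 10⁻⁶ at n=115. Under protocol 14.1.2 the imputation is by predictive mean matching, which fills in observed values. The imputed changes therefore stay five-valued, and more than 15 of 30 datasets should fail the check.

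**4. The resulting test, by section.**

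| UPS missing | SAP 7.4 | SAP 7.9.2.3 | Protocol |
|---|---|---|---|
| 5% or fewer | no imputation | paired t-test named; Wilcoxon in effect | same as SAP 7.9.2.3 |
| More than 5% | MI, pooled t-test, no check | imputation per 7.4; if the switch sentence applies, Wilcoxon with no rule for combining 30 datasets | LOCF and Wilcoxon in effect |

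The protocol route differs in data as well as test. Before month 6, UPS is collected only at baseline and month 3 (protocol Table 4), so LOCF carries one of those values forward instead of imputing month 6.

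**5. Whether the choice of test changes decisions.** n=121, two-sided 0.05, 2,000 trials per row, zeros dropped for Wilcoxon. The Monte Carlo standard error near 5% is sqrt(0.05 × 0.95/2000) = 0.5 percentage points.

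| Assumed probabilities for −2, −1, 0, 1, 2 | Mean | SD | t rejects | Wilcoxon rejects | Opposite decisions |
|---|---|---|---|---|---|
| six planned-effect sets, e.g. 0, .115, .35, .455, .08 | 0.50 | 0.80 | 100% | 100% | 0% |
| small effect | 0.24 | 0.83 | 89.4% | 88.8% | 0.7% |
| .02, .14, .68, .14, .02 | 0 | 0.66 | 5.0% | 5.0% | 0.3% |
| .1, .2, .4, .2, .1 | 0 | 1.10 | 5.5% | 5.4% | 1.0% |
| 0, .3, .5, .1, .1 | 0 | 0.89 | 4.7% | 6.0% | 3.0% |
| 0, .4, .36, .08, .16 | 0 | 1.06 | 5.5% | 8.7% | 6.8% |

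At the planned effect there were also no opposite decisions at alpha 0.0125. A separate run of 3,000 trials per scenario gave about 2% to 6% opposite decisions at true means of 0.15 to 0.20.

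**The case against.** **The SAP can be read consistently.** If the Shapiro-Wilk sentence in 7.9.2.3 covers only unimputed data, each branch has one test, Hochberg has one p-value, and no pooling rule for Wilcoxon is needed. That reading is fair, but the sentence does not state the limit. Even then, the test in effect moves from Wilcoxon to t as the count goes from six missing values to seven, with no reason given, and it still differs from protocol 14.1.2.

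**The SAP may have refined the protocol on purpose.** Protocol section 14 calls itself high-level and defers detail to the SAP, and imputation that respects the ordinal scale is a sensible refinement. This may well be so. Whether the departure is recorded cannot be judged: the SAP contents list a section 7.12 on changes to planned analysis, but its text is not in the copy reviewed.

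**Nothing changes at the planned effect.** This stands. A reader might infer that the 99% power claim fails because the t-test behind it would not be run. It does not fail: simulated power is about 100% with either test.

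**The same normality check governs UUI, UF and OAB-q.** A reader might infer that it is a defect there too. The documents do not support that as an inconsistency. For those endpoints the rule is pre-specified and reads the same in protocol and SAP, and they are not five-valued scores. Any error inflation would depend on an assumed skewness that the documents do not give. Replacing the rule there is a preference about method and is not part of this point.

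**Conclusion.** The UPS analysis is wrong as written. With more than 5% of UPS data missing (7 or more of 121), three sections lead to different confirmatory analyses. The cause is that SAP 7.4 took UPS out of the normality switch while SAP 7.9.2.3 and the protocol kept it. With 5% or fewer missing the two documents agree, so a reader who infers a three-way conflict in every case goes too far. The remaining problem in that branch is that the named paired t-test would in effect never be run.

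The size is modest. Sample size and stated power do not change, and the tests agree at mean 0.50 and SD 0.80. At null or small effects they give opposite decisions in roughly 1% to 7% of trials, and in fewer under the narrow symmetric null. With a skewed change and zero mean, rejection at nominal 5% was about 5% for t and 6% to 9% for Wilcoxon. These figures rest on assumed category probabilities, and the certainty that the switch fires is an empirical result at about this sample size. The point should be corrected because it leaves a data-dependent choice in a p-value that enters Hochberg and supports the urgency claim.

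**What to change.** Before data freeze, fix one UPS test for both missing-data branches: the t-test of mean change, as a paired t-test on complete cases and as the pooled t-test after the ordinal imputation already described in SAP 7.4. Delete the Shapiro-Wilk sentence from SAP 7.9.2.3 and from protocol 14.5.3, and report the Wilcoxon signed-rank test as a sensitivity analysis. Take urgency out of the common imputation and LOCF/Wilcoxon route in protocol 14.1.2, or record in the SAP that it departs from the protocol for UPS. Leave the rules for UUI, UF and OAB-q as they are.

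The cost is wording only, with no change to sample size, visits or data collection. The downside is that the signed-rank test, which some would prefer for an ordinal score, is no longer confirmatory. The power loss is negligible: at mean 0.24 the simulated power was 89.4% for t and 88.8% for Wilcoxon.

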## 7.5 Adjustments for Multiple Comparisons

The primary objective is the percentage of subjects considered a UUI responder at 6 months. Four secondary objectives will also be assessed, all of which will be assessed 6 months after implantation of tibial neuromodulation.

To support an indication for OAB, device effectiveness will be demonstrated for all the symptoms associated with OAB, including UUI, UF, and urgency. UUI therapy effectiveness will be demonstrated if the primary objective proportion of subjects with UUI response is greater than the performance goal (40%). UF therapy effectiveness will be demonstrated if the secondary UF objective demonstrates an improvement from baseline to 6 months in number of UF episodes. Urgency therapy effectiveness will be demonstrated if the secondary urgency objective demonstrates an improvement from baseline to 6 months in UU.

The p-values for the primary and secondary objectives will be calculated according to the methods outlined in their respective analysis sections. The p-values will be reported unadjusted and two-sided; however, declarations of statistical significance will follow the procedures laid out in this section.

The primary objective will be tested separately from the secondary objectives. If the one-sided primary objective p-value is <0.025, then the null hypothesis will be rejected, and the test will be declared statistically significant.

The Hochberg method for the multiplicity adjustment will be used to test the four secondary objective hypotheses, thereby maintaining an overall two-sided type I error rate at 0.05 for these objectives. Each p-value for the four secondary objectives will be calculated. If all p-values are less than 0.05 (two sided), all will be declared significant. If not, the p-values will be ordered from largest to smallest (identified as p1-p4 in this section). If p1 is greater than 0.05, the remaining p-values (p2, p3, p4) will be compared against an alpha of 0.025 (0.05/2). If the three remaining p-values are all less than 0.025, they will all be declared significant. If p2 is greater than 0.025, the remaining p-values (p3, p4) will be compared against an alpha of 0.017 (0.05/3). If p3 and p4 are both less than 0.017, they will both be declared significant. If p3 is greater than 0.017, p4 will be compared against an alpha of 0.013 (0.05/4). If p4 is less than 0.013, it will be declared significant.

The multiplicity adjustment will be performed for evaluations of the secondary endpoints only. No multiplicity adjustment will be performed for supporting, sensitivity, or subset analyses [REDACTED]

## 7.6 Demographic and Other Baseline Characteristics

Demographics and other baseline characteristics summarized will include:

- Age, sex, race, and ethnicity
- Years since UUI diagnosis
- Secondary diagnoses
- Body Mass Index (BMI)
- Medical history
- Steroid use and smoking status
- OAB treatment history
- Baseline UUI episodes per day (for those subjects with UUI diagnosis), baseline voids per day (for those subjects with UF diagnosis), quality of life (OAB-q HRQL score), average degree of urgency for all UI and UF episodes, and number of subjects with each urgency level on the UPS

## 7.7 Treatment Characteristics

Treatment measures summarized will include stimulation programming measures, such as programmed amplitude, pulse width, and frequency (Hz), program use, and a summary of usage data. Measures of delivered treatment will be summarized with standard descriptive statistics including means, standard deviations, medians, minimum, and maximum for each follow-up visit.

## 7.8 Interim Analyses

No interim assessment of effectiveness will be completed. Safety stopping rules are documented in the CIP.

Study progress reports will be submitted annually. Analysis for the purposes of supporting pre-market approval applications will occur once all subjects have completed the 6-month follow-up visit and will include the primary and secondary objectives and detailed safety summaries. Additional measures will be addressed based on available data at time of the pre-market approval application. A final report will be prepared once all data collection has ended and all subjects have completed the 24-month follow-up visit or have been exited. The inferential analysis for the primary and secondary objectives will not be updated for the final report.

## 7.9 Evaluation of Objectives

### 7.9.1 Primary Objective

#### 7.9.1.1 Primary Objective – UUI Responder Rate

To demonstrate that the percentage of subjects who are considered a UUI responder after 6 months of tibial neuromodulation exceeds a performance goal of 40%.

**Hypothesis:** The percentage of subjects who are considered a UUI responder 6 months after tibial neuromodulation implantation is greater than 40%.

$$H_0: p \leq 40\%$$

$$H_A: p > 40\%$$

Where  $p$  = the percentage of subjects who are UUI responders

**Endpoint Definition and Derivation:** A 3-day urinary voiding diary will be used to collect bladder symptoms, including UUI episodes. The primary objective endpoint is the proportion of tibial neuromodulation subjects considered a UUI responder at 6 months after device implant. A subject is considered a UUI responder if they meet the UUI responder criteria as defined in the voiding diary analysis section 7.2.2.

**Performance Requirements:** The null hypothesis will be rejected if the one-sided p-value is less than 0.025. Only the two-sided p-value will be reported.

**Rationale for Performance Criteria:** The proposed study design includes a primary objective performance goal of 40%. The performance goal defines an active historical control for this study and was defined to position the TNM outcome between the expected performance for medications and the more complex SNM treatment.

**Sample Size Justification:** The sample size justification for the primary objective is provided in section 6.

**Analysis Methods:** The analysis for UUI responder rate will be summarized at 6 months after implant. If 5% of the data or fewer are missing for the primary analysis, no imputation will be used, and the objective will be tested using a binomial test for the Complete Case analysis set. Otherwise, missing data will be imputed for the Full Analysis Set as specified in section 7.4, and the objective will be tested using a Z-test. The two-sided 95% confidence interval will also be provided.

**Determination of Subjects/Data for Analysis:** The primary objective analysis will include all subjects from the Full Analysis Set (i.e., all implant attempted subjects) as defined in section 7.1.3.

**Supportive and Sensitivity Analyses:** There are no requirements or expectations for the results of the supporting and sensitivity analyses. They are meant to investigate the robustness of the study results and/or to provide further details on the therapy effects.

Additional supporting analyses to further understand the primary objective will be completed through analyses of the change in UUI (secondary objective) and percentage change in UUI (additional measure).

To assess the robustness of the primary objective results under the influence of missing data, sensitivity and subgroup analyses will be conducted using alternative missing data methods and by including different subsets of subjects. The first sensitivity analysis will be completed including subjects from the Primary Objective Complete Case analysis set. This analysis set will be used for a second sensitivity analysis which will be completed including only subjects who received stimulation ('As treated analysis') at the 6-month follow-up visit. An analysis will also be completed to evaluate UUI responder rate differences between different stimulation programs, comparing stimulation programs only if there are an adequate number of subjects in each stimulation program to ensure a stable estimate of response. A tipping point sensitivity analysis will also be completed. A final sensitivity analysis will be conducted on the Primary Objective Complete Case analysis set assigning response failure for the following subjects: those who took any dose of OAB medication in the 2 weeks prior to the diary collection period, and those who received an advanced therapy at any time from implant to the 6-month follow-up visit.

Complete Case analysis set subgroup analyses will be done for the following subject groups: sex, age (divided by median age; divided by age 65), race, and ethnicity. Subjects on the demographic cut point will be added to the adjacent group containing fewer subjects. Any subgroup with less than 10 subjects will not be reported.

As an exploratory analysis to assess if treatment effect differs by study center, a supporting analysis will be completed, as described in 7.3. This analysis will test whether the treatment effect is homogeneous between study centers for the UUI responder rate at 6 months.

UUI responder rate will be assessed over time through 24 months as part of the additional measures.

